12.5.5 Primary end point-CMV disease [modified ITT group]

The primary analysis will be repeated in the modified ITT group [excludes subjects that withdrew prior to receipt of valganciclovir if in preemptive arm and subjects that have no post randomization PCR testing in the preemptive group]. An additional disease free survival model will be presented with censoring at retransplantation [return to standard care] if retransplantation occurs greater than 30 days post enrollment.

12.5.6 End point committee and investigator-determined CMV disease

The primary analysis will be repeated separately utilizing the adjudicated incidence of CMV disease and the investigator-determined CMV disease as the end point.

12.6 Secondary outcome measures

12.6.1 Clinical outcomes

12.6.1.1 Incidence of late onset CMV disease [adjudicated]

The incidence of adjudicated CMV disease will be determined at the 3 and 12-month time points (late-onset CMV disease) using an analysis similar to that specified for the primary analysis of the primary endpoint and, in addition, will include separate subset analyses for CMV syndrome and CMV tissue invasive disease. The analysis will be a Cochran-Mantel-Haenszel test of the significance of the odds ratio, while controlling for the use of induction antibody therapy and renal dialysis. In addition potential prognostic factors, such as allograft rejection will be examined with a Cox proportional hazards model applied to the ITT and modified ITT populations. This analysis will be used to test the presence of a treatment effect while controlling for the various prognostic factors entered into the model. Results will be reported as the hazard ratio comparing two groups.

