3.2.2 Secondary outcome measures (compared between 2 groups)

1. Clinical outcomes within 12 months post-transplant
 - Incidence of late-onset CMV disease (CMV disease occurring after 100 days post-randomization)
 - Incidence of major bacterial, fungal, and non-CMV viral infections
 - Incidence of allograft rejection
 - Incidence of graft loss (retransplantation)

- All-cause mortality
- 2. Hematologic toxicity (assessed until 107 days post-enrollment)
 - Incidence of neutropenia (ANC <1,000 and <500/ μ L)
 - Hematopoietic growth factor (granulocyte colony stimulating factor) for neutropenia - (receipt of hematopoietic growth factor during study days 1-107)

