5.4.2 Randomization

Subjects will be randomized in 1:1 allocation to one of 2 study groups. All subjects that have met all criteria for study enrollment and have given written informed consent will be randomized via a web-based randomization system at the study web-portal.

The study team member randomizing the subject will get an immediate message providing group assignment. Randomization at each site will be stratified by: 1) the receipt of lymphocyte depleting induction and 2) dialysis at time of randomization. Randomization will occur as soon as it is feasible, but no later than 10 days after transplantation. Inadvertently randomized

subjects who do not meet the inclusion/exclusion criteria or those who are withdrawn prior to receiving the study drug will be replaced.

Subjects receiving lymphocyte depleting induction at the time of transplantation (even for those randomized to the preemptive therapy group) may receive up to 10 days of antiviral therapy with valganciclovir or IV ganciclovir after transplantation. Additionally, if the treating physician prescribes valganciclovir or IV ganciclovir for any length of time prior to randomization, it will not preclude subject enrollment. For subjects assigned to the prophylaxis group, the first dose of study drug should be given on the day of randomization regardless of lymphocyte induction. For subjects in the preemptive group that have received lymphocyte depleting induction, antiviral therapy with valganciclovir or IV ganciclovir will be given for ten days then stopped. Subjects that have not received lymphocyte depleting induction, but have received doses of valganciclovir or IV ganciclovir after transplantation prior to randomization, will have the pre-randomization treatment stopped and begin study treatment on randomization day based on their assigned group.

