12.6.1.4 Allograft rejection

Rejection will be evaluated by several methods. Rejection rates at one year, between the two groups will be evaluated with a CMH test, both non-stratified and adjusted for receipt of antilymphocyte induction and renal dialysis. Initial rejection will be evaluated in a time dependent Cox model with the end point being the date first rejection episode. The starting point will be date of transplantation and the rejection free survival functions will be compared between the two regimens adjusted for cluster. Multiple rejection episodes will be evaluated by comparing the total 1 year episodes of rejection between the regimens using a regression model with the endpoint total number of rejection episodes, clustered by site, and adjusted for receipt of antilymphocyte induction therapy and renal dialysis. An additional model may be developed to adjust for inequalities not adequately controlled by the randomization process. Incidence of chronic graft rejection will be compared between the two study groups using a CMH test stratified for receipt of induction lymphocyte depleting therapy and controlling for renal dialysis.

Rejection episodes

Incidence rates will [number of rejection episodes per patient days of follow up] will be calculated and compared between the two groups. Patient days will be counted from the day of

randomization until the date of death, one year or last known follow up if subject is unable to be followed for one year.

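### The supplementary Cox model for late-onset CMV disease adjusts the treatment comparison for allograft rejection, a post-randomization outcome, which can bias its hazard ratio

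*Combined protocol and SAP*

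**What the plan says.** Section 12.6.1.1 first gives late-onset CMV disease a "Cochran-Mantel-Haenszel test of the significance of the odds ratio, while controlling for the use of induction antibody therapy and renal dialysis". These are the two randomization strata in section 5.4.2: "1) the receipt of lymphocyte depleting induction and 2) dialysis at time of randomization".

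It then adds a second analysis: "potential prognostic factors, such as allograft rejection will be examined with a Cox proportional hazards model applied to the ITT and modified ITT populations". Its purpose is stated: "This analysis will be used to test the presence of a treatment effect while controlling for the various prognostic factors entered into the model". So is its output: "Results will be reported as the hazard ratio comparing two groups". Section 12.6.1.2 repeats the analysis for adjudicated and for investigator-determined disease.

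Elsewhere rejection is an outcome. Section 3.2.2 lists "Incidence of allograft rejection" within 12 months among the secondary measures compared between groups, and section 12.6.1.4 says: "Initial rejection will be evaluated in a time dependent Cox model with the end point being the date first rejection episode". On timing, section 5.4.2 says: "Randomization will occur as soon as it is feasible, but no later than 10 days after transplantation".

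Section 12.6.1.1 does not limit the covariate to rejection before randomization. It does not say whether rejection enters as a fixed or a time-dependent variable, it leaves the covariate list open, and it does not label the hazard ratio as a conditional or direct effect.

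**The concern.** A covariate measured after randomization can carry part of the treatment effect, or can be a consequence of the outcome. The documents give grounds for concern on several routes:

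- **Strategy to rejection.** The trial compares rejection between arms, so it treats this effect as an open question. If rejection also raises the risk of CMV disease, adjustment removes the part of the effect that acts through rejection.
- **Shared causes.** Section 2.2.1 names intensity of maintenance immunosuppression as a possible confounder in the pilot data. It could plausibly drive both rejection and CMV disease. If strategy also affects rejection, conditioning on rejection links strategy to that unmeasured cause.
- **CMV to rejection.** Section 2.1 lists rejection among the indirect consequences of CMV. With ever/never coding, rejection that followed CMV disease would enter as a predictor of it.
- **Rejection to antiviral exposure.** Under section 6.2.4, rejection treated with a lymphocyte-depleting agent leads to antiviral drug in either group.

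At stake is the interpretation of one reported hazard ratio, for the secondary outcome listed first in section 3.2.2.

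**Working it through.** **No figure to reproduce.** The documents give no planned estimate, rejection rate or covariate effect for this model. The inputs below are assumptions unless a section is cited.

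**1. Timing.** Randomization is at most 10 days after transplant and rejection is counted to 12 months, so at least 355 of 365 days of the rejection window follow randomization.

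**2. Simple arithmetic for mediation.** Suppose there is no direct effect of strategy, a proportion p of each arm has rejection, and rejection multiplies the CMV hazard by k. Treating rejection as present from the start of the late-onset window, the total hazard ratio is roughly

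[(1 − p₁) + p₁k] / [(1 − p₀) + p₀k],

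and the rejection-adjusted hazard ratio is about 1.00.

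| p₁ vs p₀ | k | Total HR | Adjusted HR |
|---|---|---|---|
| 30% vs 20% | 3 | 1.6/1.4 = 1.143 | about 1.00 |
| 30% vs 20% | 2 | 1.3/1.2 = 1.083 | about 1.00 |
| 20% vs 30% | 3 | 1.4/1.6 = 0.875 | about 1.00 |
| 20% vs 20% | 3 | 1.4/1.4 = 1.000 | about 1.00 |

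**3. Simulation.** Ten runs of 6,000 subjects per scenario, with follow-up for late-onset disease from day 100 to day 365. The reference arm had about 25% one-year rejection and about 20% late CMV disease before any rejection effect. The shared cause, where present, is a normal log-hazard term with SD 0.8 acting on both events.

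| Strategy on rejection hazard | Rejection on CMV hazard | Direct HR | Other | HR without rejection | HR with ever-rejection | HR with time-dependent rejection |
|---|---|---|---|---|---|---|
| ×1 | ×2 | 0.25 | none | 0.256 | 0.255 | 0.254 |
| ×1 | ×2 | 0.25 | CMV triples rejection hazard | 0.260 | 0.260 | 0.258 |
| ×1 | ×1 | 0.25 | CMV quadruples rejection hazard | 0.242 | 0.244 | 0.243 |
| ×0.6 | ×3 | 0.25 | none | 0.238 | 0.256 | 0.255 |
| ×0.6 | ×3 | 1 | none | 0.919 | 1.006 | 1.007 |
| ×1.7 | ×3 | 1 | none | 1.121 | 0.996 | 0.990 |
| ×0.6 | ×1 | 1 | shared cause | 1.012 | 1.066 | 1.050 |
| ×0.3 | ×3 | 1 | shared cause | 0.850 | 1.098 | 1.082 |

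The true total hazard ratio in the seventh row is 1.00, so 1.012 shows the simulation noise. The shift appears when strategy affects rejection and is negligible when it does not. Its direction follows the direction of that effect. CMV-to-rejection feedback alone moved little here. Time-dependent coding did not remove the shift.

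**4. Against the trial's precision.** Section 12.1 assumes 20% and 5% with 80 per group, so 16 and 4 events over 12 months. The late-onset subset cannot be larger.

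- 16 vs 4 events: SE(log HR) ≈ √(1/16 + 1/4) = 0.56.
- 16 vs 16 events: √(1/16 + 1/16) = 0.35.
- Shift from 0.238 to 0.256: ln(0.256/0.238) = 0.073, and 0.073/0.56 = 0.13 SE.
- Shift from 1.143 to 1.00: 0.134, which is 0.24 SE (÷0.56) to 0.38 SE (÷0.35).
- Largest simulated shift, from 0.850 to 1.098: 0.256, and 0.256/0.35 = 0.73 SE. This needs strategy to cut the rejection hazard to 0.3 times.

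**The case against.** The strongest reply has four parts.

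- **A clean comparison already exists.** The CMH test for this endpoint uses only the stratification factors, and the Cox model is an addition. Section 12.7.1.1 also gives a Cox model for time to CMV disease adjusted for site, induction and dialysis, with no mention of rejection. This stands. A reader might infer that late-onset disease has no randomized comparison, or that the primary analysis in section 12.5.4 is compromised. The documents support neither. Section 12.7.1.1 covers all CMV disease to 12 months, however, so it does not replace a late-onset hazard ratio.
- **Strategy may not affect rejection.** Section 2.2.1 cites liver data showing no difference in rejection with oral ganciclovir prophylaxis against placebo, and no significant impact of prophylaxis in a large registry. This makes a large shift less likely. These are not comparisons of prophylaxis with preemptive therapy, and the trial itself tests the question.
- **The sizes are hypothetical and small.** This also stands. Near the design hazard ratio of .229 the simulated shift was 0.13 SE, which would rarely change a conclusion.
- **The coding is unspecified.** Rejection after CMV disease enters only under fixed ever/never coding, so that route is an ambiguity and not a stated error. Time-dependent coding would answer that route only.

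None of this explains why an outcome belongs among the covariates of a model declared to test the treatment effect.

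**Conclusion.** The concern holds for the supplementary Cox model in section 12.6.1.1 and its repetition under section 12.6.1.2. As written, the plan can yield a between-group hazard ratio that is not a clean randomized comparison. It would be wrong to say that the hazard ratio is certainly biased. Size and direction depend on the effect of strategy on rejection, the effect of rejection on CMV disease, shared causes and timing, and the documents quantify none of these. Under the assumed inputs the shift ran from negligible (0.256 to 0.255) through 0.92 to 1.01 and 1.12 to 1.00, up to 0.85 to 1.10 in an extreme case. The CMH test for the endpoint and the primary analysis are unaffected. The text should be corrected before analysis, but the point does not threaten the trial's main conclusion.

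**What to change.** In section 12.6.1.1, and so in section 12.6.1.2:

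1. Restrict the Cox model that tests the treatment effect to a closed, pre-specified list of baseline covariates: lymphocyte-depleting induction, dialysis at randomization, and site handled as in section 12.7.1.1. Any further factor should be measured before randomization and named in advance. The design rates imply at most about 20 events (16 + 4), so the list should be short.
2. Move rejection to a separate exploratory association model, entered as a time-dependent covariate that changes at the date of first rejection. State that no treatment effect is claimed from that model. Time-dependent coding alone, inside the treatment-effect model, is not enough.

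The cost is SAP wording only. Section 12.6.1.4 already uses the date of first rejection, so no new data are needed. The sample size, the CMH test and the primary analysis do not change.

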12.6.1.2 Incidence of late onset of CMV disease [adjudicated and investigator-determined]

The above analysis will be repeated separately utilizing adjudicated CMV disease and investigator determined CMV disease as the respective endpoint.

12.6.1.3 Bacterial, fungal and non-CMV viral infections

Invasive fungal infections, major bacterial infections and non-CMV viral infections will be analyzed. These infections are outlined in the manual of operations. The analysis of incidence of an opportunistic infection will be performed using a Chi Square test or Fisher Exact in the modified ITT population. Results will be reported as the p -value and the 95% confidence interval for the difference in the rates of invasive fungal, major bacterial or viral infections; the analysis will be repeated using a CMH test stratified by receipt of induction therapy. The analysis will include an assessment of baseline comparability of the comparison groups and will incorporate variables not adequately controlled by randomization. The initial episode of major infection will be evaluated in a time dependent Cox model with the end point being the date of first major infection. The starting point will be date of transplantation and the infection free survival functions will be compared between the two regimens adjusted for cluster [site]. Subjects will be censored at death and study termination/withdrawal. Multiple infection episodes will be evaluated by comparing the total 1 year episodes per person day of follow up between the two regimens. The analysis will be repeated controlling for receipt of anti-lymphocyte induction and renal dialysis. The type of infection (major bacterial, fungal, non- CMV viral) will be compared between the two regimens using a CMH test, non-stratified and controlled for induction antilymphocyte therapy and renal dialysis. Summary tables listing the type of opportunistic infections for each regimen will be presented.

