6.2.2.1 Prophylaxis group

Subjects assigned to the prophylaxis arm will receive valganciclovir at a dose of 900 mg po qd (adjusted for renal dysfunction). Study drug will be given on the day of randomization (considered Day 1 of the study) and will be administered for 100 days.

For subjects randomized to the prophylaxis group that have been receiving prophylaxis therapy for CMV as part of their standard care prior to randomization, the prophylaxis dose will not be repeated on study day 1 if a dose has already been administered. However, if a dose was given as standard care, the dose will be counted as the 1st day of the 100 days of study treatment doses.

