constitute a separate informed consent document. Subjects will have the choice to opt out of genetic testing although take part in all other aspects of the CAPSIL study. This blood sample will be obtained at the transplant center. Samples will be coded with subject study numbers. Sites will freeze samples per tube manufacturer's specifications and retain on site until shipped to the [name] Lab at Fred Hutchinson Cancer Research Facility.

Genetic samples are not time sensitive or dose dependent and therefore may be drawn at any time point after consent for this sampling is obtained. This genetic sample may therefore be drawn with eligibility labs (pre-randomization) or the next scheduled standard of care blood draw (pre or post-study drug administration) to avoid unnecessary blood draw. If a sample is drawn pre-randomization and the subject is not eligible for randomization (screen failure), the genetic sample should be destroyed as per the institutions policy.

7. 5 Treatment phase (study days 1-100)

7. 5.1 Prophylaxis group only

Subjects assigned to the prophylaxis group will initiate valganciclovir at a dose of 900 mg po qd (adjusted for renal dysfunction) on study day 1. For subjects randomized to the prophylaxis group that have been receiving prophylaxis therapy for CMV as part of their standard care prior to randomization, the prophylaxis dose will not be repeated on study day 1 if a dose has already been administered. However, if a dose was given as standard care, the dose will be counted as the 1st day of the 100 days of study treatment doses.

7. 5.2 Preemptive therapy group only

Subjects assigned to the preemptive therapy group will undergo weekly CMV PCR assessments beginning on study Day 7. Preemptive treatment group will begin preemptive antiviral drug therapy during study days 1-100 only when viremia is detected by weekly surveillance and will continue preemptive therapy until two consecutive weekly CMV PCRs are negative. Valganciclovir 900 mg po bid (dose adjusted for renal function) will be employed upon detection of CMV viremia (at any level) and started within one week of initial positive PCR and continued until two consecutive tests performed one week apart are negative. Therapy may be repeated if further detection of viremia is detected during the 100 day period.

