7,14,21,28,35,42,49,56,63,70,77,84,91,98. All sample windows are +/-3 days. CMV PCR samples will be obtained at the transplant center if hospitalized, or will be collected during routine care follow-up clinic appointments and outpatient laboratories, skilled nursing facilities, or rehabilitation facilities. CMV PCR analysis will be completed at the University of Washington Medical Center Virology lab.

CMV PCR results will be faxed to the study site within 24 hours of receipt of blood if received Monday through Saturday. Samples received on Sundays or holidays will be resulted within 48 hours or the next business day. CMV PCR surveillance must continue at weekly intervals in preemptive subjects if continuing valganciclovir therapy after day 98 until two consecutive negative results weekly.

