12.3.2 Modified intent-to-treat population

The modified ITT population will consist of those subjects in ITT population who were randomized and received at least one dose of valganciclovir in the prophylaxis group or had at least one CMV PCR test post-randomization in the preemptive therapy group.

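### The infection-incidence test in section 12.6.1.3 is specified only in a modified ITT population whose arm-specific entry rule drops early losses almost entirely from the preemptive arm; ITT should be its main population.

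*Combined protocol and SAP*

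**What the plan says.** Major bacterial, fungal and non-CMV viral infection within 12 months is a secondary outcome (section 3.2.2). Section 12.6.1.3 specifies that the main test of its incidence is performed "using a Chi Square test or Fisher Exact in the modified ITT population". The Cox model for first infection, the episode-rate comparison and the type-of-infection CMH test in the same section name no population.

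Section 12.3.2 defines the modified ITT as ITT subjects who "received at least one dose of valganciclovir in the prophylaxis group or had at least one CMV PCR test post-randomization in the preemptive therapy group". The two qualifying events fall at different times:

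- **Prophylaxis.** Section 6.2.2.1: "Study drug will be given on the day of randomization (considered Day 1 of the study".
- **Preemptive.** Section 7.5.2: "Subjects assigned to the preemptive therapy group will undergo weekly CMV PCR assessments beginning on study Day 7". Section 7.5.3.2 adds: "All sample windows are +/-3 days".

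Section 12.3.1 keeps every eligible, consented and randomized subject in the ITT population, whether or not they were dosed or assessed after baseline. Section 12.3 commits to an ITT analysis for the primary endpoint only. Section 12.7.1.7 lists opportunistic infection rates as an exploratory endpoint in both the ITT and modified ITT populations.

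Section 12.5.5 restates the modified ITT exclusions in other terms. Its first exclusion reads "excludes subjects that withdrew prior to receipt of valganciclovir if in preemptive arm". Its second covers preemptive subjects with no post-randomization PCR.

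**The concern.** A prophylaxis subject who takes the day 1 dose and dies on day 3 stays in the infection analysis. A preemptive subject with the same course drops out of it, although that subject missed nothing the assigned strategy required. Entry thus depends, in one arm only, on remaining alive and in the study until the first PCR.

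Such losses are plausible. Randomization falls within 10 days of transplant, section 5.3 excludes only a life expectancy under 72 hours, and section 9.4.1.1 describes the population as critically ill. The outcome is also one on which the strategies could differ in either direction: section 2.2.1 notes that prophylaxis is considered to have the greater effect on indirect CMV outcomes. An exclusion that depends on arm and on post-randomization events should not sit under the main test of that outcome.

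**Working it through.** The documents give no infection rate, early-loss rate or power figure for this endpoint, so there is no stated figure to reproduce. The check compares the timing of the two entry rules and then sizes the effect under stated assumptions.

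**Timing**

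- Prophylaxis qualifies on day 1 (section 6.2.2.1).
- Preemptive routinely qualifies on day 7 ± 3, that is days 4 to 10 (sections 7.5.2 and 7.5.3.2).
- Gap: 4 − 1 = 3 days to 10 − 1 = 9 days.

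**Effect on the preemptive rate**

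Inputs:

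- n = 88 per arm, from the minimum enrollment of 176 at 1:1 (sections 4 and 5.4.2).
- p = 30%, the same true one-year infection rate in both arms (assumed).
- L = preemptive subjects lost before any PCR (assumed, 1 to 8).
- f = share of those L who had an infection before leaving (assumed, 0 to 1).

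The modified ITT preemptive rate is (n·p − L·f)/(n − L), with n·p = 88 × 0.30 = 26.4. The prophylaxis rate stays at 30%. For L = 2, f = 1: (26.4 − 2)/86 = 28.4%, a shift of −1.6 points. For L = 2, f = 0: 26.4/86 = 30.7%, a shift of +0.7.

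The type I error of the nominal two-sided 0.05 test is taken by normal approximation:

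1 − Φ((1.96·SE0 − d)/SE1) + Φ((−1.96·SE0 − d)/SE1)

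Here d is the difference in rates, SE0 the pooled and SE1 the unpooled standard error. For L = 4, f = 1, the rates are 0.300 (n = 88) and 22.4/84 = 0.267 (n = 84). Then d = 0.0333, SE0 = 0.0688 and SE1 = 0.0687, and the error is 0.070 + 0.007 = 0.077.

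| L | Shift, f = 0 | Shift, f = 0.5 | Shift, f = 1 | Type I error (f = 0; 0.5; 1) |
|---|---|---|---|---|
| 1 | +0.3 | −0.2 | −0.8 | 0.050; 0.050; 0.052 |
| 2 | +0.7 | −0.5 | −1.6 | 0.051; 0.051; 0.056 |
| 4 | +1.4 | −1.0 | −3.3 | 0.055; 0.052; 0.077 |
| 8 | +3.0 | −2.0 | −7.0 | 0.070; 0.059; 0.174 |

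Shifts are in percentage points. With p at 20% or 40% instead, and L = 1 or 2, the shift stays between +0.9 and −1.9 points.

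**Direction**

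Setting (n·p − L·f)/(n − L) = p gives f = p. The exclusion lowers the preemptive rate only if infection is more common among the early losses than in the arm as a whole; otherwise it raises it. For example, take 35 of 88 infected (39.8%) and three lost. If all three were infected the rate becomes 32/85 = 37.6%; if one was, 34/85 = 40.0%; if none was, 35/85 = 41.2%.

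**The two definitions side by side**

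Section 12.3.2 drops never-dosed prophylaxis subjects and preemptive subjects without a PCR. Section 12.5.5 attaches both exclusions to the preemptive arm and does not mention undosed prophylaxis subjects. Preemptive subjects receive valganciclovir only on viremia, so its first exclusion, taken literally, would remove a never-viremic preemptive subject who withdraws months later.

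**The case against.** Four stronger readings are tempting, and the documents do not support them.

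- **That infections are never compared in ITT.** Section 12.7.1.7 compares rates in both populations, and three analyses in section 12.6.1.3 name no population. This stands as a limit on the point. Section 12.7.1.7 is nevertheless exploratory and per patient-day, and it gives separate rates only for bacterial and fungal infections. It does not replace an ITT test of the secondary incidence endpoint.
- **That only the preemptive arm loses subjects.** Section 12.3.2 also drops never-dosed prophylaxis subjects. A PCR for suspected CMV disease, allowed from day 1 (section 7.6.4), can qualify a preemptive subject early. Almost entirely is accurate; only is not.
- **That sick or infected subjects are removed.** Infection or deterioration alone removes no one. Hospitalized subjects have the PCR drawn at the transplant center (section 7.5.3.2). Only those with no PCR at all are dropped, mainly through death or withdrawal.
- **That the rule favours preemptive therapy.** This would need f above p. A subject who leaves in the first week has had little time to record an infection, so the shift could go the other way.

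It is also fair to say that the effect is small beside sampling error. The standard error of the difference at 30% is √(2 × 0.3 × 0.7/88) = 6.9 points. The first exclusion in section 12.5.5 may be a slip of arm name, and it concerns the primary endpoint. It still leaves two incompatible descriptions of the population that section 12.6.1.3 relies on.

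Extending the point to neutropenia is weak. Section 12.6.2.1 rests on protocol safety labs, first due after baseline on day 7 (section 7.5.3.1), so adding subjects without labs would only count unmeasured people as non-events.

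**Conclusion.** The point holds in a limited form. The main incidence test for a secondary endpoint is specified in the modified ITT alone, and that population's entry rule removes early deaths and withdrawals almost entirely from the preemptive arm. This departs from the randomized comparison for no stated reason. The direction is not established. Under the assumed 30% rate and 88 per arm, one or two losses shift the preemptive rate by about 2 points or less, with type I error at most 0.056. The effect becomes material only with about four to eight losses that were mostly infected: 3 to 7 points, type I error 0.077 to 0.174. The infection rate, number of losses and infected share are all assumptions, since the documents give none of them. The change is worth making because it is cheap and removes the differential exclusion outright, not because a large bias has been shown.

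**What to change.** 1. In section 12.6.1.3, make ITT (all randomized subjects) the main population for infection incidence and keep the modified ITT as a sensitivity analysis.
2. Apply the same population to the Cox, episode-rate and type-of-infection analyses.
3. Reconcile the exclusions in section 12.5.5 with section 12.3.2, so that the modified ITT has one definition.
4. State how subjects without follow-up are counted. Section 5.4.3.3 stops follow-up for those who discontinue before study drug. Taken literally, this may affect the preemptive arm more, since its subjects receive study drug only on viremia. The rule in section 12.5.4 is available: death or loss without the event counts as no event, with a second analysis counting losses as events.
5. Leave neutropenia and growth factor use as planned, or add ITT there only as a sensitivity analysis.

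The cost is SAP wording. Section 7.7.3 already records outcomes from randomization, so early deaths need no new data. The small downside is the rule in item 4: ITT restores the denominator but does not recover outcomes that were never collected.
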